## 1. LIST OF ABBREVIATIONS

Abbreviation	Term
ACEI	Angiotensin converting enzyme inhibitor
AE	Adverse event
AEOI	Adverse events of interest
ALP	Alkaline phosphatase
ALT	Alanine aminotransferase
AR(1)	first-order autoregressive
ARB	Angiotensin receptor blocker
AST	Aspartate aminotransferase
ATC	Anatomical Therapeutic Chemical
BP	Blood pressure
CI	Confidence interval
CS	Compound symmetry
CSR	Clinical study report
CTCAE	Common Terminology Criteria for Adverse Events
eCRF	Electronic case report form
eGFR	Estimated glomerular filtration rate
FAS	Full Analysis Set
FMV	First morning void
IgAN	Immunoglobulin A nephropathy
IQR	Interquartile range
LS	Least squares
MedDRA	Medical Dictionary for Regulatory Activities Terminology
MLD	Maximum labeled dose
MMRM	Mixed model repeated measures
NT-proBNP	N-terminal prohormone of brain natriuretic peptide
PPAS	Per Protocol Analysis Set
PT	Preferred term
RAASi	renin-angiotensin-aldosterone system inhibitor
SD	Standard deviation
SAP	Statistical analysis plan
SEM	Standard error of the mean
SGLT2	sodium glucose cotransporter-2
SMQ	Standardized MedDRA Query

Abbreviation	Term
SOC	System organ class
TEAE	Treatment-emergent adverse event
UA/C	Urine albumin-to-creatinine ratio
ULN	Upper limit of normal
UP/C	Urine protein-to-creatinine ratio
WHO	World Health Organization

## 2. INTRODUCTION

The purpose of this statistical analysis plan (SAP) is to describe the statistical methods and technical specifications for the analysis of data collected for the sparsentan in combination with sodium glucose cotransporter-2 (SGLT2) inhibition in the treatment of adult participants with immunoglobulin A nephropathy (IgAN).

Any deviation from this plan will be documented in the clinical study report (CSR).

Protocol Revision Chronology		
Original Protocol	13 February 2023	Original

### **3. STUDY OBJECTIVES AND ENDPOINTS**

#### **3.1. Study Objectives**

##### **3.1.1. Primary Efficacy Objective**

The primary efficacy objective of the study is to evaluate the effect of sparsentan on albuminuria in participants with IgAN on SGLT2 inhibitor medication.

##### **3.1.2. Secondary Efficacy Objective**

The secondary efficacy objective of the study is to evaluate the effect of sparsentan on proteinuria variables, estimated glomerular filtration rate (eGFR) and blood pressure (BP), in participants with IgAN on SGLT2 inhibitor medication over the duration of the study.

##### **3.1.3. Safety Objective**

The safety objective of the study is to assess the safety and tolerability of sparsentan in participants with IgAN on chronic stable treatment with an SGLT2 inhibitor.

### **3.2. Study Endpoints**

#### **3.2.1. Efficacy Endpoints**

##### **3.2.1.1. Primary Efficacy Endpoint**

The primary efficacy endpoint is

- The change from baseline in urine albumin-to-creatinine ratio (UA/C) at Week 24.

##### **3.2.1.2. Secondary Efficacy Endpoints**

The secondary efficacy endpoints including the following:

- Achievement of UA/C of <0.2 g/g at Week 24.
- Achievement of 30% and 50% reduction from baseline in UA/C at Week 24.
- The change from baseline in UA/C, urine protein-to-creatinine ratio (UP/C), eGFR, and BP at each visit.

#### **3.2.2. Safety Endpoints**

Safety endpoints include the following:

- The incidence of treatment-emergent adverse events (TEAEs), serious adverse events (AEs), AEs leading to treatment discontinuation, and adverse events of interest (AEOI).
- Changes from baseline in body weight, vital signs, physical examinations, peripheral edema, and clinical laboratory parameters.

## 4. STUDY DESIGN

### 4.1. Summary of Study Design

This is a 28-week, open-label, multicenter, single-group, Phase 2 exploratory study to determine the safety and effect of sparsentan in participants with IgAN who are at risk of disease progression despite being on both stable renin-angiotensin-aldosterone system inhibitor (RAASi) and SGLT2 inhibitor treatment for at least 12 weeks prior to study entry.

Approximately 60 participants aged  $\geq 18$  years will be enrolled into this study.

[figure not shown]
Participants who provide written informed consent will be assessed for eligibility and will undergo baseline evaluations including clinical laboratory tests. Per the eligibility criteria, all participants are required to be on a stable dose(s) of angiotensin converting enzyme inhibitor (ACEI) and/or angiotensin receptor blocker (ARB) and on a stable dose of a SGLT2 inhibitor at screening and will continue their stable treatments through the screening period. Eligible participants entering the study will remain on the stable dose of the SGLT2 inhibitor for the duration of the study, however, they will discontinue ACEI and/or ARB therapy before the Day 1 visit. The final dose of an ACEI and/or ARB should be taken on the day before the Day 1 visit. Baseline evaluations will be taken on Day 1 prior to administration of the first dose of the study medication (sparsentan).

Study medication will be administered daily for a treatment period of 24 weeks with study visits conducted at weeks 2-, 4-, 12-, and 24- following Day 1. Following the 24-week treatment period, study medication will be discontinued for 4 weeks. At this time, the Investigator should resume standard of care treatment, including RAASi treatment. Participants will return to the site for a visit at Week 28 for the safety follow-up visit.

UA/C and UP/C will be determined using first morning void (FMV) samples and will be calculated as the average of 2 FMV samples collected within 3 days prior to each visit. If 1 of the samples is missing, UA/C and UP/C from the single sample will be used.

The overall study design is summarized in Figure 1 (below). For individual participants, the total duration of participation from the screening visit to the safety follow-up visit (Week 28) will be a maximum 34 weeks.

**Figure 1: Study Design**

Abbreviations: ACEI = angiotensin converting enzyme inhibitor; ARB = angiotensin receptor blocker; mg = milligrams; SGLT2i = sodium glucose cotransporter-2 inhibitor; SOC = standard of care.

## **4.2. Definition of Study Medication**

Study interventions are all pre-specified, investigational, and non-investigational medicinal products, medical devices, and other interventions (eg, surgical, and behavioral) intended to be administered to the study participants during the study conduct.

At the Week 1 the starting dose will be 1 tablet ( $1 \times 200$  mg) taken prior to the morning meal.

Starting at week 3 the dose will be titrated to 1 tablet ( $1 \times 400$  mg) taken prior to the morning meal, if tolerated and determined safe by the Investigator.

Patients can continue initial dose without titration or have dose reductions back to the initial dose (reduced dose) after dose titration based on tolerability as described in the protocol.

## **4.3. Sample Size Considerations**

### **4.3.1. Sample Size Justifications**

Approximately 60 participants will be enrolled in the study. The sample size of the study is determined empirically without formal statistical assumptions. A sample size of 60 is sufficient to detect at least 1 AE with probability 95%, assuming an expected AE incidence of 5% using the binomial distribution.

## **4.4. Randomization**

This is a single-arm study; therefore, randomization is not applicable in this study.

## **5. PLANNED ANALYSES**

### **5.1. Primary Analysis**

The primary analysis will be conducted on the Full Analysis Set (FAS) after all participants complete their safety follow-up visit (Week 28) or have discontinued study.

All analysis on efficacy and safety endpoints will be conducted.

### **5.2. Interim Analysis**

An interim analysis will be performed 24 weeks after approximately 20 participants have been enrolled to evaluate select safety and efficacy endpoints.

### **5.3. Change from Planned Protocol Analyses**

The analyses specified in this SAP are consistent with Original Protocol. There are no changes from the planned protocol analyses.

## **6. GENERAL CONSIDERATIONS FOR DATA ANALYSES AND HANDLING**

### **6.1. General Presentation Considerations**

Individual patient data obtained from electronic case report forms (eCRFs), central laboratories, local laboratories, external sources, and derived data will be presented in data listings by patient.

All outputs will be incorporated into Microsoft Word rich text format files, sorted, and labeled according to the International Council for Harmonisation recommendations, and formatted to the appropriate page size(s).

Tabulations will be produced for appropriate demographic, baseline, efficacy, and safety parameters.

For categorical variables, summary tabulations of the number and percentage of patients within each category (with a category for missing data) of the parameter will be presented.

For continuous variables, the number of patients, mean (arithmetic), standard deviation (SD), standard error of the mean (SEM), median, interquartile range (IQR), minimum, and maximum values will be presented. Geometric mean and geometric coefficient of variation will additionally be presented for key efficacy variables (eGFR and quantitative urinalysis, including UP/C and UA/C). The precision of summary statistics, unless otherwise specified, will be as follows: mean, median, and IQR to 1 more decimal place than the raw data and SD and SEM to 2 decimal places more than the raw data. In general, the decimal places should not exceed 3 decimal places unless appropriate.

Confidence intervals (CIs) will be provided and will be rounded to 1 decimal place, unless otherwise specified in the table and listing shell.

### **6.2. Data Conventions**

The precision of original measurements will be maintained in summaries, when possible.

For tables where rounding is required, rounding will be done at the final stage of the calculation to the nearest round-off unit. For example, when rounding to the nearest integer, values  $\geq XX.5$  will be rounded up to  $XX + 1$  (eg, 97.5 will round up to 98), while values  $< XX.5$  will be rounded down to  $XX$  (eg, 97.4 will round down to 97).

Percentages based on frequency counts will be based on available data, and denominators will exclude missing values, unless otherwise stated. For frequency counts of categorical variables, categories whose counts are zero will be displayed for completeness. For example, if none of the patients discontinue due to “lost to follow-up,” this reason will be included in the table with a count of zero. Percentages will be presented as a whole number (no decimal places), and nonzero values less than 0.5% will be presented as “<1%.” Values <100% but that round up from 99.5% to 100% will be presented as “>99%.”

Quantitative laboratory tests containing less than (<) and greater than (>) symbols are test results that are below and above quantifiable limits, respectively. To retain these values for analysis purpose, values will be imputed as the numeric portion of the result.

## **6.3. Analysis Population**

### **6.3.1. Full Analysis Set**

All participants who take at least 1 dose of sparsentan will be included in the FAS. All efficacy and safety analyses will be based on the FAS.

### **6.3.2. Per Protocol Analysis Set**

The Per Protocol Analysis Set (PPAS) is a subset of the FAS containing participants who meet study eligibility requirements and have no protocol deviations that might impact the assessment of efficacy measurements. The PPAS will be used for sensitivity analyses relating to efficacy.

## **6.4. Baseline Definition**

### **6.4.1. General**

Unless otherwise defined, study baseline is defined as the last nonmissing assessment prior to first dose of study medication and including the baseline (Day 1) visit.

### **6.4.2. Quantitative Urinalysis Parameters**

Baseline for quantitative urinalysis parameters, including UA/C and UP/C, will be calculated as the average of the 2 FMV samples collected within 3 days prior to the Day 1 visit. If one of the samples is missing, the single sample will be used.

## **6.5. Derived and Transformed Data**

### **6.5.1. Baseline Age**

Age is captured in the electronic data capture system as relative to the date of informed consent.

### **6.5.2. Standard Calculations**

Variables requiring calculation will be derived using the following formulas:

- Days – A duration expressed in days between 1 date (*date 1*) and another later date (*date 2*) will be calculated using the following formulas:  
$$\text{duration in days} = \text{date2} - \text{date1} + 1$$
- Weeks – A duration expressed in weeks is calculated as the number of days divided by 7
- Months – A duration expressed in months is calculated as the number of days divided by 365.25/12 (approximately 30.4)
- Years – A duration expressed in years is calculated as the number of days divided by 365.25
- Height – Height entries made in inches (in) are converted to centimeters (cm) using the following formula:  
$$\text{height (cm)} = \text{height (in)} \times 2.54$$

- Weight – Weight entries made in pounds (lb) are converted to kilograms (kg) using the following formula:  
weight (kg) = weight (lb) / 2.2046
- Temperature – Temperature entries in degrees Fahrenheit are converted to degrees Celsius using the following formula:  
temperature (degrees Celsius) = 5 / 9 × (temp [degrees Fahrenheit] – 32)
- Change from baseline – Change from baseline will be calculated as:  
Change = post baseline value – baseline value
- Percent change from baseline – Percent change from baseline will be calculated as:  
Percent change = ([post baseline value – baseline value]/baseline value) × 100

For variables requiring log transformation, natural log will be used.

### 6.5.3. Visit Windows

A visit window method will be applied to determine the record to be used for analysis across the study period for efficacy and safety endpoints based on laboratory results, including eGFR and quantitative urinalysis (including UP/C and UA/C). If a patient has multiple assessments (including unscheduled visits) within the visit window, the value closest to the target day for that visit will be selected for analysis. If more than 1 assessment is equidistant to the target day, then latest value will be selected.

The visit window shown in Table 1 is defined for endpoints based on laboratory results.

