7.1. Discontinuation of Study Intervention

During the course of the study, it may be necessary for a participant to permanently discontinue study intervention prematurely. If study intervention is permanently discontinued prematurely, the participants should return to the site for a visit as close as possible to the participant's last dose of study intervention. This visit may be a regularly scheduled visit or an unscheduled visit, and all assessments for this visit are to be completed per the regular scheduled visit or the Week 24 visit/EOT for an unscheduled visit, respectively, as listed in the SoA ([Section 1.3](#)). At this visit, the primary reason for premature discontinuation from study intervention, will be recorded on the EOT eCRF. Following this visit, participants are to complete the safety

follow-up visit as listed in the SoA ([Section 1.3](#)) within approximately 4 weeks after the last dose of study intervention.

The discontinuation of the SGLT2 inhibitor at any point during the study is not a reason for participant removal from protocol-required investigational product(s) or procedural assessments.

Reasons for removal from protocol-required investigational product(s) or procedural assessments include any of the following:

- Decision by Sponsor.
- Lost to follow-up.
- Death.
- Ineligibility determined.
- Protocol deviation.
- Noncompliance.
- Adverse event.
- Participant request.
- Pregnancy.
- Receipt of a kidney transplant or initiation of chronic dialysis.
- Diagnosis of NYHA Class II-IV CHF.
- Hyperkalemia that is resistant to treatment (see [Section 10.8](#)).

The need for additional intervention for the treatment of IgAN or the occurrence of safety endpoints are not, by themselves, criteria for discontinuation of study intervention.

The primary reason for discontinuation of study intervention, will be recorded on the EOT eCRF. Subsequent study visit data will be recorded on the visit specific eCRF (either a regular scheduled visit or unscheduled visit). Once the EOT eCRF is completed, study intervention cannot be resumed.

Additional details regarding temporary interruption or permanent discontinuation of the study intervention are outlined in [Section 7.1.2](#) and [Section 7.2](#).

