**Table 1: Visit Window**

Analysis Visit	Relative Target Day	Analysis Visit Window (Study Days)	
		eGFR and Safety Labs	Quantitative Urinalysis
Week 2	15	2 – 22	N/A
Week 4	29	23 – 57	2 – 57
Week 12	85	58 – 127	58 – 127
Week 24	169	128 – 183	128 – 183
Week 28	197	>183	>183

eGFR = estimated glomerular filtration rate; N/A = Not applicable

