## 8. EFFICACY

### 8.1. General Considerations

All efficacy analyses will be done descriptively on the FAS using observed data only. Change from baseline (or percent change from baseline, as appropriate) will be summarized with mean and 95% CI, as appropriate. For categorical efficacy endpoints, the proportion of participants in the category will be presented along with corresponding 95% CI.

The primary and secondary efficacy endpoint analyses based on the PPAS will be performed as sensitivity analyses. All primary efficacy analyses based on laboratory data will use central laboratory data only.

Albuminuria (UA/C) and proteinuria (UP/C) will be determined based on a FMV samples. As UA/C and UP/C are highly right-skewed variables, analyses will be performed on log-transformed data. For ease of interpretation, results will be presented in the original units.

The eGFR for each baseline and post-baseline visit will be determined using the Chronic Kidney Disease Epidemiology Collaboration ([Levey 2009](#)) formula for adults based on serum creatinine values from the visit.

For the purposes of efficacy analyses, an assessment is considered “on treatment” if it occurs after the first dose of study medication and no more than 3 days after last dose of study medication for the patient. Additionally, efficacy analyses may be repeated using all on-study data.

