## **9.5. Clinical Laboratory Evaluations**

Laboratory parameters will be summarized in the standard international system of units. Quantitative laboratory results will be summarized using descriptive statistics at baseline and at each post-baseline scheduled visit. Both absolute and percentage change from baseline will also be summarized.

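### By-visit safety laboratory tables have no treatment-status rule, so an early stopper's off-drug follow-up sample is filed under a treatment week and can displace the on-drug end-of-treatment value

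*SAP*

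**What the plan says.** **Window rule.** SAP 6.5.3 selects laboratory records "across the study period for efficacy and safety endpoints based on laboratory results, including eGFR and quantitative urinalysis (including UP/C and UA/C"). Unscheduled visits count. Within a window, "the value closest to the target day for that visit will be selected for analysis", and "If more than 1 assessment is equidistant to the target day, then latest value will be selected".

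**Windows.** SAP Table 1 has one column for eGFR and safety laboratories and one for quantitative urinalysis. Both are defined by study day, with no condition on whether the participant is still taking sparsentan.

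**Early stopping.** Under Protocol 7.1, after permanent discontinuation "the participants should return to the site for a visit as close as possible to the participant's last dose of study intervention". A safety follow-up visit then takes place "within approximately 4 weeks after the last dose of study intervention". The Schedule of Activities includes clinical laboratory tests, eGFR and quantitative urinalysis at that follow-up visit. Its footnote g expects standard of care to restart after Week 24/EOT, with the RAAS inhibitor at the investigator's discretion.

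**On-treatment limit.** SAP 8.1 states, for efficacy analyses, that an assessment is on treatment if it comes after the first dose and "no more than 3 days after last dose of study medication for the patient". SAP 8.2.1 applies an on-treatment policy to the primary analysis.

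**Safety laboratories.** SAP 9.5 states: "Quantitative laboratory results will be summarized using descriptive statistics at baseline and at each post-baseline scheduled visit". It sets no on-treatment limit.

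**The concern.** Change from baseline in laboratory parameters is a named safety endpoint. A reader of a Week 12 or Week 24 row will take it to describe participants about 12 or 24 weeks into sparsentan. Under the rule as written, the row can include potassium, creatinine, hemoglobin or liver values taken about four weeks after the drug was stopped, possibly after a RAAS inhibitor was restarted.

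The rule can also discard the EOT value. That is the last value on drug, and for someone who stopped because of a laboratory problem it is probably the most informative one. The Week 28 row in turn holds mainly completers and says little about recovery in those who stopped.

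A second question concerns efficacy. The SAP does not give the order of the 3-day limit and the window selection. If selection comes first, the off-drug sample can win its window and then be removed by the limit, and a valid on-treatment UA/C or eGFR value is lost with it.

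**Working it through.** **1. The plan's own figures.** The Table 1 target days are 15, 29, 85, 169 and 197. The midpoints between neighbours are (15+29)/2 = 22, (29+85)/2 = 57, (85+169)/2 = 127 and (169+197)/2 = 183. These are exactly the upper limits in Table 1, so the windows are consistent and depend on calendar day only.

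**2. Where the follow-up sample lands.** Let L be the last-dose day and put the follow-up at L + 28.

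| Last dose | Follow-up day | Table 1 window |
|---|---|---|
| up to 29 | up to 57 | Week 4 |
| 30–99 | 58–127 | Week 12 |
| 100–155 | 128–183 | Week 24 |
| 156 or later | 184 or later | Week 28 |

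With a gap of 21 or 35 days (the ±7-day visit window, taken as an assumption for early stoppers), the latest L that still falls in Week 24 is 162 or 148.

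**3. Which value is selected (safety laboratory column).** Assumptions: scheduled samples on Days 15, 29 and 85 while on drug, an EOT sample on Day L + 1, follow-up at L + 28, and L from 10 to 155 (146 stop days).

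| Last dose | Window of follow-up sample | Selected value | Stop days |
|---|---|---|---|
| 10–21 | Week 4 | off-drug, only value | 12 |
| 22–29 | Week 4 | on-drug | 8 |
| 30–56 | Week 12 | off-drug, only value | 27 |
| 57–70 | Week 12 | off-drug, displaces on-drug | 14 |
| 71–99 | Week 12 | on-drug | 29 |
| 100–126 | Week 24 | off-drug, only value | 27 |
| 127–154 | Week 24 | off-drug, displaces on-drug | 28 |
| 155 | Week 24 | on-drug | 1 |

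Off-drug selected: 12 + 27 + 14 + 27 + 28 = 108 of 146 (74%). On-drug value displaced: 14 + 28 = 42 of 146 (29%). On the other 66 days the window holds no on-drug value.

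**4. Sensitivity to the gap.**

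| Gap (days) | Off-drug selected | On-drug displaced | Filed as Week 28 |
|---|---|---|---|
| 21 | 99 (68%) | 47 | 0 |
| 28 | 108 (74%) | 42 | 0 |
| 35 | 113 (77%) | 33 | 7 |

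Placing the EOT sample on the last-dose day itself gives 100, 111 and 114 selected, so the result does not depend on that choice.

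**5. One participant.** Last dose Day 140, EOT sample Day 141, follow-up Day 168. Distances to target 169 are |141 − 169| = 28 and |168 − 169| = 1. The Day 168 sample becomes the Week 24 value and the Day 141 sample is not used in that row.

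**6. Efficacy and the order of the two rules.** A sample 21 to 35 days after the last dose fails the 3-day limit whichever rule runs first, so no off-drug follow-up value enters the on-treatment analyses of UA/C, UP/C or eGFR. The order matters only when an on-drug value shares the window.
- Limit first: the Day 141 value is kept.
- Selection first: Day 168 is chosen and then removed, and Day 141 is lost.

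At a 28-day gap the second order would lose an on-treatment value on 42 of 146 stop days for eGFR. For urine it is 47 of 146; the Week 4 urine window opens on Day 2, which adds last-dose Days 10–14.

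**The case against.** **Efficacy is protected.** A reader might infer that the on-treatment laboratory analyses, including the primary endpoint, are contaminated with off-drug values. They are not. SAP 8.1 and 8.2.1 exclude these samples from the on-treatment efficacy analyses, and SAP 9.5 never calls its tables on-treatment. This stands in full.

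**Safety signals have other routes.** Shift tables to the worst value (SAP 9.5.1 and 9.5.2), liver threshold counts (9.5.3), AEOIs and the summaries of TEAEs, including hyperkalemia, hepatic and anemia terms, do not depend on window selection. It would be tempting to say that the trial's safety signal is diluted. The documents do not support that: peaks are still captured, and the direction of any shift in by-visit means is unknown, since values may recover off drug or move again if a RAAS inhibitor is restarted.

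**All-data summaries by study day are a legitimate convention.** This is true, and the plan does collect data after discontinuation. But convention does not explain why a follow-up sample should replace an EOT sample in the same window.

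**SAP 9.5 speaks of scheduled visits.** One could read this as the recorded visit, which would keep the follow-up sample separate. However, SAP 6.5.3 names safety endpoints and Table 1 has a column for safety laboratories, so the windows govern as written. The two sections should be reconciled.

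**Order of the rules.** On-treatment status is defined for each assessment, so applying the limit first is the natural reading. The loss of efficacy values is a possibility left open, not a demonstrated loss.

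**Conclusion.** The point holds for the by-visit safety laboratory summaries. Following SAP 6.5.3 as written, the follow-up sample of a participant whose last dose is on or before Day 155 is filed under Week 4, 12 or 24 at a 28-day gap. It is the selected value on 108 of 146 stop days and displaces an on-drug value on 42. At gaps of 21 and 35 days the figures are 99 and 47, and 113 and 33. At 35 days the sample does reach Week 28 on 7 stop days, so it is not true at every gap that it never gets there.

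A reader might turn 74% into a number of participants. The documents give no discontinuation rate and no distribution of stopping times, and not every stopper will attend follow-up, so no such count can be supported. The shares also assume scheduled visits on their target days.

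For efficacy, what remains is an unstated order of operations. It should be settled before the analysis because it can decide whether an on-treatment UA/C or eGFR value is used. The study is descriptive with no hypothesis test, so no decision rule is at risk. The correction is still worth making: about 60 participants are planned, and a few misfiled records could be visible in a by-visit summary.

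**What to change.** In SAP 6.5.3, state the order of steps:

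1. Classify each post-baseline laboratory record with the SAP's existing limit: more than 3 days after the last dose is off treatment.
2. Apply Table 1 to on-treatment records only, for the efficacy analyses and for the by-visit safety laboratory summaries in SAP 9.5.
3. Summarise off-treatment records as a separate safety follow-up visit, defined relative to the last dose.

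Add a reference from SAP 9.5 to this rule. Keep the worst-value and last-value shift tables, and the optional repeat of the efficacy analyses on all on-study data, on all records.

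The cost is one or two sentences and a programming rule, with no new data. The Week 4, 12 and 24 safety tables will hold slightly fewer values, and an EOT sample taken more than 3 days after the last dose will move to the follow-up row.
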